9.0 TREATMENT/INTERVENTION PLAN

Patients who have signed the consent form and are deemed eligible for this clinical trial will start therapy with the following schedule:

- Length of cycle: 28 days. Treatment window for day 1 of start of each cycle is +/- 7 days. Treatment window for intra-cycle carfilzomib and/or daratumumab doses is +/- 2 days.
- These cycles will consist of:

Cohort 1

- Cycle 1 ONLY: Daratumumab 16 mg/kg days 1, 8, 15, and 22; Carfilzomib 20 mg/m² per dose, days 2 and 3; Carfilzomib 36 mg/m² per dose, days 8, 9, 15, and 16; Dexamethasone 20 mg/dose, days 1, 2, 3, 8, 9, 15, 16 and 22; Lenalidomide 25 mg/day, days 2 – 21 every 28 days; Acetaminophen 650 mg; intravenous Diphenhydramine 25 mg. Montelukast 10 mg will be administered prior to the first 4 doses of Daratumumab.
- Cycle 2: Daratumumab 16 mg/kg days 1, 8, 15, and 22; Acetaminophen 650 mg; intravenous Diphenhydramine 25 mg.
- Cycles 3-6: Daratumumab 16 mg/kg days 1 and 15; Acetaminophen 650 mg; intravenous Diphenhydramine 25 mg.
- Cycles 7-8: Daratumumab 16 mg/kg day 1; Acetaminophen 650 mg ; intravenous Diphenhydramine 25 mg.
- Cycles 2-8: Carfilzomib 36 mg/m² per dose, days 1, 2, 8, 9, 15, and 16
- Cycles 2-8: Lenalidomide 25 mg/day, days 1-21 every 28 days
- Cycles 2: Dexamethasone 20 mg/dose, days 1, 2, 8, 9, 15, 16 and 22
- Cycles 3-4: Dexamethasone 20 mg/dose, days 1, 2, 8, 9, 15 and 16
- Cycles 5- 8: Dexamethasone 10 mg/dose, days 1, 2, 8, 9, 15 and 16

Cohort 2

- Cycle 1 ONLY: Daratumumab 16 mg/kg days 1, 8, 15, and 22; Carfilzomib 20 mg/m² per dose, day 2; Carfilzomib 56 mg/m² per dose, days 8 and 15; Dexamethasone 20 mg/dose, days 1,2, and 22, 40 mg/dose days 8 and 15 ; Lenalidomide 25 mg/day, days 2–21 every 28 days; Acetaminophen 650 mg; intravenous Diphenhydramine 25 mg. Montelukast 10 mg will be administered prior to the first 4 doses of Daratumumab.
- Cycle 2: Daratumumab 16 mg/kg days 1, 8, 15, and 22; Acetaminophen 650 mg; intravenous Diphenhydramine 25 mg.

- Cycles 3-6: Daratumumab 16 mg/kg days 1 and 15; Acetaminophen 650 mg; intravenous Diphenhydramine 25 mg.
- Cycles 7-8: Daratumumab 16 mg/kg day 1; Acetaminophen 650 mg; intravenous Diphenhydramine 25 mg.
- Cycles 2-8: Carfilzomib 56 mg/m² per dose, days 1, 8, and 15
- Cycles 2-8: Lenalidomide 25 mg/day, days 1-21 every 28 days
- Cycles 2: Dexamethasone 40 mg/dose, days 1, 8, and 15; 20 mg/dose day 22
- Cycles 3-4: Dexamethasone 40mg/dose, Days 1, 8 15
- Cycles 5-8: Dexamethasone 20mg/dose, Days 1, 8, 15
- After receiving 4 or more cycles, patients who are considered to be eligible for subsequent high dose therapy/autologous stem cell transplant (ASCT) will be recommended to undergo autologous stem cell harvesting for potential use in the future. For patients who choose to undergo stem cell harvest, the subsequent cycle may be delayed for up to 7 weeks.

Cohorts 1, and 2

- Patients achieving ≥PR at end of 4 cycles will continue to receive the planned total of 8 cycles of combination therapy.
- Patients <PR after completing 4 cycles will go off study therapy.
- After completion of protocol therapy, patients will remain on study for an additional 3 years for survival analysis, including annual MRD assessment when appropriate.

Daratumumab was FDA approved for the indication of relapsed myeloma in November 2015. The initial approval was single drug used for 3rd line therapy. In October of 2016 FDA label was updated to include daratumumab with Revlimid/dexamethasone as 2nd line therapy; also the updated FDA label include daratumumab with Velcade/dexamethasone as 2nd line therapy. In June 2017, the FDA label was updated again; daratumumab with Pomalidomide/dexamethasone as 2nd line therapy. There is an ongoing randomized phase 3 study investigating daratumumab with Revlimid/dexamethasone as front line therapy. The drug combination we are testing (carfilzomib, daratumumab with Revlimid/dexamethasone) has been assessed in a phase 1 study which was recently presented at ASCO in June 2017.²⁵ In the phase 1 trial the dosing of carfilzomib was 70 mg/m² once a week; we are planning on giving 36 mg/m² twice a week in cohort 1 since that is the NCCN approved dose and 56mg/m² once a week in cohort 2.

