- Two-cohort, two-stage phase II trial of combination therapy (daratumumab, carfilzomib, lenalidomide, and dexamethasone [DKRd]) for newly diagnosed multiple myeloma patients
- Each cycle consists of 28 days
- After 4-6 cycles of therapy, transplant eligible patients will undergo stem cell collection
- Pre- and post-treatment bone marrow biopsies will be obtained for confirmation of diagnosis and correlative studies
- Patients will receive 8 cycles of induction combination therapy of DKRd. Patients will undergo evaluation for response at monthly intervals using IMW uniform response criteria (Kumar. et al. Lancet Oncol 2016) with SPEP, 24-hr UPEP (if applicable), serum free light chains (FLC), and immunofixation.
- Patients with <PR at completion of 4 cycles, will stop therapy and be taken off study treatment at completion of 4 cycles.
- Patients achieving >PR at end of 4 cycles, will continue to receive the planned total of 8 cycles of combination therapy
 - Patients obtaining CR/sCR at any point during cycles 1-8 in serum and urine will undergo MRD testing using multi-parametric flow cytometry.
- Upon completion of protocol therapy, eligible patients will be encouraged to proceed onto maintenance therapy or high dose therapy with stem cell rescue under a separate treatment protocol or standard of care. If clinically indicated, patients may need alternative therapy.
- After completion of protocol therapy, patients will remain on study for an additional 3 years for survival analysis, including annual MRD assessment when appropriate.

Treatment Plan (see schema below)

Cohort 1:

- Cycle 1 ONLY: Daratumumab 16 mg/kg days 1, 8, 15, and 22; Carfilzomib 20 mg/m² per dose, days 2 and 3; Carfilzomib 36 mg/m² per dose, days 8, 9, 15, and 16; Dexamethasone 20 mg/dose, days 1,2, 3, 8, 9, 15, 16, and 22 ; Lenalidomide 25 mg/day, days 2–21 every 28 days; Acetaminophen 650 mg; intravenous Diphenhydramine 25 mg. Montelukast 10 mg will be administered prior to the first 4 doses of Daratumumab.
- Cycle 2: Daratumumab 16 mg/kg days 1, 8, 15, and 22; Acetaminophen 650 mg; intravenous Diphenhydramine 25 mg.

- Cycles 3-6: Daratumumab 16 mg/kg days 1 and 15; Acetaminophen 650 mg; intravenous Diphenhydramine 25 mg.
- Cycles 7-8: Daratumumab 16 mg/kg day 1; Acetaminophen 650 mg; intravenous Diphenhydramine 25 mg.
- Cycles 2-8: Carfilzomib 36 mg/m² per dose, days 1, 2, 8, 9, 15, and 16
- Cycles 2-8: Lenalidomide 25 mg/day, days 1-21 every 28 days

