9.4 Monitoring

- 9.4.1 Routine labs (CBC, chemistry panel 14, LDH, magnesium, uric acid, phosphate) will be performed at baseline and on Day 1, 2, 8, 15, and 22 of cycle 1 and Day 1 of each cycle thereafter, end of therapy, and 1-year and 3-year after end of therapy. Myeloma tests include serum protein electrophoresis, serum immunofixation, beta-2 microglobulin, quantitative immunoglobulins and serum free light chains assay will be performed at baseline and Day 1 of each cycle, end of therapy, and 1-year and 3-year after end of therapy. Serum Lymphocyte subsets will be performed at baseline, Day 1 of cycle 4, and end of treatment. Routine labs, myeloma labs, and lymphocyte subsets can be performed 24 hrs in advance.
- 9.4.2 For patients with initial baseline 24-hr UPEP samples demonstrating ≥ 100 mg/24 hrs, patients will continue to have 24-hr UPEP samples day 1 of each cycle. Once 24-hr UPEP is < 100 mg/24 hrs, patient can have random UPEP with IFE until achieving negativity. If initial baseline 24-hr UPEP sample is IFE positive and/or < 100 mg/24, patients can have random UPEP samples with IFE until achieving negativity. Once random UPEP and IFE is negative, no further urine samples are needed (unless patient's disease is primarily measurable by 24 hr urines i.e. oligosecretory/hyposecretory)
- 9.4.3 Patients will have clinic visits with H&P or standard progress notes assessing for toxicity/side effects on Day 1, 8, and 15, of cycle 1 and Day 1 of each cycle thereafter 1-month after end of therapy, 1-year after end of therapy and 3-year after end of therapy. Treatment window for day 1 of start of each cycle is ± 7 days. Treatment window for intra-cycle carfilzomib doses is ± 2 days. Vital signs will be checked prior to administration of study drugs carfilzomib or daratumumab in all cycles.

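### The ±7-day window for Day 1 has no tighter early limit: a start 7 days early is permitted, removes the lenalidomide rest and, at Cycles 2 and 3, lands on the previous Day 22 daratumumab date

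*Combined protocol and SAP*

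**What the plan says.** Section 1.0 gives the nominal cycle: "Each cycle consists of 28 days". Section 9.0 then sets two windows: "Treatment window for day 1 of start of each cycle is +/- 7 days" and "Treatment window for intra-cycle carfilzomib and/or daratumumab doses is +/- 2 days". Section 9.4.3 repeats the first as "Treatment window for day 1 of start of each cycle is ± 7 days". Footnote l of Section 10.0 repeats both, after allowing the same 7 days either way for scheduled visits.

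The dosing lines that matter, all in Section 9.0, are:

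- Lenalidomide: "Cycles 2-8: Lenalidomide 25 mg/day, days 1-21 every 28 days". Cycle 1 runs from Day 2 to Day 21.
- Daratumumab: "Cycle 1 ONLY: Daratumumab 16 mg/kg days 1, 8, 15, and 22" and "Cycle 2: Daratumumab 16 mg/kg days 1, 8, 15, and 22". Cycles 3-6 use Days 1 and 15, and Cycles 7-8 use Day 1 only.
- Dexamethasone: Day 22 is a dosing day in Cycles 1 and 2 of both cohorts, for example "Dexamethasone 20 mg/dose, days 1, 2, 3, 8, 9, 15, 16 and 22" in Cohort 1, Cycle 1. It is not one from Cycle 3 on.

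The conditions for starting a cycle are neutrophil and platelet counts on Day 1 (9.2.1) and recovery from Grade 3 or higher toxicity (9.3.1).

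**The concern.** The window is symmetric, but the two sides have different consequences. A late start lengthens the rest between cycles; an early start shortens it. The early allowance of 7 days equals the whole lenalidomide rest period. It also equals the distance from Day 22 to the next nominal Day 1, which matters at the starts of Cycles 2 and 3 because Cycles 1 and 2 include Day 22 daratumumab and dexamethasone.

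Within a cycle the plan limits daratumumab spacing through the ±2-day window. At the boundary between cycles it sets no comparable limit. A start at −7 would therefore comply with the protocol and would not count as a deviation. What is at stake is patient safety and dose intensity at the cycle boundary, not the analysis.

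**Working it through.** The plan states no figure for the shortest interval between cycles, so there is none to reproduce. The check is calendar arithmetic on the Section 9.0 schedule, with the previous cycle started and dosed on schedule.

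Let k be the number of days by which the next cycle starts early. The nominal next Day 1 is Day 28 + 1 = Day 29 of the previous cycle.

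- Next Day 1 = Day 29 − k
- Lenalidomide-free days (last dose Day 21) = (29 − k) − 21 − 1 = 7 − k
- Dose per unit time relative to plan, for the shortened cycle = 28/(28 − k)
- Daratumumab gap at the Cycle 2 or 3 start, previous dose on Day 22 = (29 − k) − 22 = 7 − k
- The same gap if that dose slipped to Day 24 under the ±2-day window = (29 − k) − 24 = 5 − k

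| k | Next Day 1 | Lenalidomide-free days | Dose per unit time | Daratumumab gap from Day 22 | Daratumumab gap from Day 24 |
|---|---|---|---|---|---|
| 0 | Day 29 | 7 | 1.000 | 7 | 5 |
| 2 | Day 27 | 5 | 28/26 = 1.077 | 5 | 3 |
| 3 | Day 26 | 4 | 28/25 = 1.120 | 4 | 2 |
| 7 | Day 22 | 0 | 28/21 = 1.333 | 0 | not applicable |

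**Lenalidomide.** A previous cycle of 2-7 contains 21 × 25 = 525 mg. That averages 525/28 = 18.75 mg/day as planned and 525/21 = 25 mg/day at k = 7.

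**Daratumumab at k = 7.** The ±2-day window can bring the Day 22 dose forward, but only to gaps of 22 − 21 = 1 day or 22 − 20 = 2 days. Within a cycle the shortest gap is Day 8 + 2 = Day 10 to Day 15 − 2 = Day 13, which is 3 days.

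**Which cycles.** The loss of lenalidomide rest applies to every start of Cycles 2-8. The Day 22 overlap applies only to the starts of Cycles 2 and 3. For Cycles 4-7 the last scheduled daratumumab dose is on Day 15, so the gap at k = 7 is 22 − 15 = 7 days. For Cycle 8 it is 22 − 1 = 21 days.

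**Whole course.** Eight cycles last 8 × 28 = 224 days. One start at −7 makes this 217 days, and 224/217 = 1.032. Cumulative dose is unchanged.

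**Anchor.** The plan does not say whether the window is counted from the actual previous Day 1 or from the original calendar. Under a calendar count, a +7 start followed by a −7 start puts the two Day 1s 28 − 14 = 14 days apart, which is inside the 21 lenalidomide days.

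**The case against.** The strongest counter-argument is that the lenalidomide line carries its own 28-day interval and that footnote l introduces the window as visit flexibility, so a 21-day cycle was never intended. That may well be the intent. The wording does not secure it: Section 9.0 calls it a treatment window, places it directly after the cycle length, and so defines a permitted departure from the 28-day schedule.

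A second argument is that safeguards exist. The count criteria and toxicity holds act on the main hazards. The one-month lenalidomide supply limit (5.2.4) and monthly REMS counseling (Appendix A) make a 21-day restart less likely. This stands as a reason to expect few such starts, but none of these rules sets an earliest date.

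A third argument concerns size. The 33% figure describes one cycle, and the overall change from one early start is about 3%. That is correct and limits the weight of the point.

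A reader might infer that the protocol directs two daratumumab infusions on one date. It does not: the Day 22 dose and the next Day 1 are separate scheduled doses, and they meet only if the full early allowance is used. Nor do the documents show that a patient who passes the Day 1 criteria is harmed by a shorter rest.

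**Conclusion.** The point holds as a minor one. The stated window permits a cycle start on Day 22, which leaves no lenalidomide-free days at any of Cycles 2-8. At Cycles 2 and 3 it also allows a daratumumab gap shorter than any the plan allows within a cycle.

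The figures assume that the previous cycle ran on schedule and that a single start is early; no accumulation over cycles is assumed. The documents do not say how often cycles start early, so the expected effect cannot be estimated.

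A reader might go further and infer a threat to the primary result. The documents do not support this. Section 14.0 counts patients who reach MRD negativity within 8 cycles, not within a number of calendar days, so the two-stage thresholds and error rates are untouched.

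**What to change.** Add one sentence in Section 9.0, Section 9.4.3 and footnote l: *Day 1 dosing of Cycles 2-8 must not occur earlier than 26 days after the actual previous Day 1.* Leave the +7-day late side and its anchor as they are. Keep Day 1 laboratory tests tied to the actual dosing day, drawn up to 24 hours before as Section 9.4.1 allows, so that the 9.2.1 counts remain current.

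Twenty-six days after Day 1 is Day 27, the k = 2 row above. This keeps at least 5 lenalidomide-free days when lenalidomide is taken on schedule, and at least 3 days between daratumumab doses. At k = 3 the gap could be 2 days. The 3-day figure is a benchmark for consistency with the plan's own within-cycle window; the documents do not establish it as a safety threshold.

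A minimum interval is better than re-anchoring the whole window to the previous Day 1. If the plan now counts from the calendar, re-anchoring would let late starts accumulate to 7 × 7 = 49 days over seven starts, against 7 days. The minimum interval also remains workable under a calendar count: after a +7 start, the latest permitted next start is 28 days later, which still leaves Days 26 to 28 after the previous Day 1.

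The cost is less room to start a cycle early or to catch up after a late start. Toxicity holds and the stem cell harvest delay of up to 7 weeks keep their own rules.

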9.1 Dose Modifications

Dose reductions are not permissible for daratumumab. Below are dose reductions for the other drugs used on this protocol.

9.1.1 Dose Reductions for Lenalidomide

	Lenalidomide
Baseline dose	25 mg
One level dose reduction	20 mg
Two level dose reduction	15 mg
Three level dose reduction	10 mg
Four level dose reduction	5 mg

9.1.2 Dose Reductions for Carfilzomib

	Carfilzomib
Baseline dose	36 mg/m ²
One level dose reduction	27 mg/m ²
Two level dose reduction	20 mg/m ²

	Carfilzomib
Baseline dose	56 mg/m ²

	Carfilzomib
One level dose reduction	45 mg/m ²
Two level dose reduction	36 mg/m ²
Three level dose reduction	27 mg/m ²
Four level dose reduction	20 mg/m ²

9.1.3 Dose Reductions for Dexamethasone

	Dexamethasone
Baseline dose	20 mg
One level dose reduction	10 mg
Two level dose reduction	4 mg
Three level dose reduction	0 mg

** Note: Dexamethasone dose may be further reduced at investigator's discretion**

	Dexamethasone
Baseline dose	40mg
One level dose reduction	20mg

Two level dose reduction	5 mg
Three level dose reduction	0 mg

** Note: Dexamethasone dose may be further reduced at investigator's discretion**

9.1.4 Infusion Related Reaction (IRR) Management - Daratumumab

Severe infusion reactions associated with Daratumumab include bronchospasm, hypoxia, dyspnea, hypertension, laryngeal edema and pulmonary edema. Signs and symptoms may include respiratory symptoms, such as nasal congestion, cough, throat irritation, as well as chills, vomiting and nausea. Less common symptoms were wheezing, allergic rhinitis, pyrexia, chest discomfort, pruritus, and hypotension. Patients will be pre-medicated with antihistamines, antipyretics and corticosteroids and frequently monitored during entire infusion. Infusions will be interrupted for interactions of any severity and medical management will be managed. Daratumumab will be permanently discontinued for life-threatening (Grade 4) reactions. For patients with Grade 1, 2, or 3 reactions, the infusion rate will be reduced when re-starting the infusion.

To reduce the risk of delayed infusion reactions, corticosteroids will be given to all patients. Patients with a history of chronic obstructive pulmonary disease may require additional post-infusion medications to manage respiratory complications. In these instances post-infusion short and long-acting bronchodilators, and inhaled corticosteroids medications may be prescribed. If the patient experiences no major infusion reactions, following the first four infusions, these additional inhaled post-infusion medications may be discontinued.

9.2. Hematologic Toxicity

9.2.1 On day 1 of each new cycle, patients must meet the following criteria:

- $ANC \geq 1.0 \times 10^9 /L$
- Platelet count $\geq 50 \times 10^9 /L$

9.2.2 If these conditions are not met on Day 1 of a new cycle:

- The next cycle of treatment will not be initiated until the above conditions (section 9.3.1) are met. If ANC and platelet counts do not satisfy the requirements above after 2 weeks of withholding treatment, the subject will go off therapy. Transfusions and growth factors are permissible.
- For patients not meeting day 1 criteria (section 9.3.1) for two cycles (non-consecutive), the study drug dose(s) will be modified for the next cycle based on dose reduction tables of section 9.2.

9.2.3 If a patient develops thrombocytopenia or neutropenia during the cycle, then the following actions would take place (see Thrombocytopenia/Neutropenia table below).

Thrombocytopenia	Lenalidomide	Carfilzomib
Fall to $< 25 \times 10^9/L$	Hold both Lenalidomide and Carfilzomib, follow CBC at least weekly or more frequently if clinically indicated. Hold prophylactic anti-coagulation.	
Return to $\geq 25 \times 10^9/L$	Resume lenalidomide at next dose reduction	Resume carfilzomib at full dose.*
Subsequent fall to $< 25 \times 10^9/L$	Hold both Lenalidomide and Carfilzomib, follow CBC at least weekly or more frequently if clinically indicated. Hold prophylactic anti-coagulation.	
Return to $\geq 25 \times 10^9/L$	Resume lenalidomide at next dose level reduction	Resume carfilzomib at full dose.*

*Carfilzomib may be dose reduced at the clinical discretion of investigator.

Neutropenia (Absolute Neutrophil Count)	Lenalidomide	Carfilzomib
Falls to $< 0.5 \times 10^9/L$ or to $< 1.0 \times 10^9/L$ with fever	Hold Lenalidomide and Carfilzomib. Add filgrastim if Grade 3 with fever (single temperature of $38.3^\circ C$ or sustained temperature of $38^\circ C$ for > 1 hour) or Grade 4. Follow CBC at least weekly or more frequently if clinically indicated.	
Returns to $\geq 1.0 \times 10^9/L$	Resume Lenalidomide at next dose reduction.	Resume Carfilzomib at full dose.*
Subsequent drop to $< 0.5 \times 10^9/L$ or to $< 1.0 \times 10^9/L$ with fever	Hold Lenalidomide and Carfilzomib. Add filgrastim if Grade 3 with fever or Grade 4. Follow CBC at least weekly or more frequently if clinically indicated.	
Returns to $\geq 1.0 \times 10^9/L$	Resume Lenalidomide at next dose reduction.	Resume Carfilzomib at full dose.*

*Carfilzomib may be dose reduced at the clinical discretion of investigator.

9.3 Non-Hematologic Toxicities Requiring Dosing Modifications

- 9.3.1 Any \geq Grade 3 toxicity require appropriate study drug to be held until resolved to Grade 1 or baseline (unless specified below in tables 9.4.4) prior to resuming therapy or initiating next cycle. Investigator will determine which drug will be held based on side effect profile and clinical judgment. If therapy has been held for more than 2 weeks due to non-hematologic toxicity, the patient will be removed from protocol therapy.

- 9.3.2 Protocol therapy will be withheld for patients who require treatment of Grade 3 infection. If therapy has been held for more than 3 weeks due to treating a grade 3 infection, the patient will be removed from protocol therapy.
- 9.3.3 For patients experiencing \geq grade 3 toxicity (unless specified below in tables 9.4.4), subsequent doses will be reduced at next dose level (according to the tables in section 9.2) if the adverse event was deemed to be attributed to study drugs. If the adverse event was deemed to be unrelated to study drugs, the patient may continue the full dose.
- 9.3.4 Electrolyte or metabolic abnormalities that are reversible with electrolyte replacement within 48 hours or $<$ grade 3 infections that can be controlled by appropriate therapy are exempt from holding treatment or dose modifications.

Lenalidomide Toxicities	Specific Dosing Modifications
Blistering Rash (Any Grade)	Discontinue lenalidomide and remove patient from therapy
Venous thrombosis/embolism	Hold lenalidomide and start therapeutic anticoagulation. Restart lenalidomide at investigator's discretion at current dose level.
Renal Dysfunction CrCl based on Cockcroft-Gault formula: $\text{CrCl} = (140 - \text{Age}) \times \text{Mass (in kilograms)} \times [0.85 \text{ if Female}] \div 72 \times \text{Serum Creatinine (in mg/dL)}$	
 CrCl 31-60 mL/min – Dose reduce lenalidomide to 10 mg daily from Days 1-21 CrCl ≤ 30 mL/min (not requiring dialysis) – Dose reduce Lenalidomide to 15 mg every 48 hours CrCl ≤ 30 mL/min (requiring dialysis) – Decrease Lenalidomide to 5 mg daily and on dialysis days give lenalidomide dose after dialysis.
Infection (\geq Grade 3)	
Hold therapy, treat underlying infection.
 
Remove patient from therapy if treatment of grade 3 infection persists for more than 3 weeks.

Carfilzomib Toxicities	Specific Dosing Modifications
Allergic Reaction/Hypersensitivity	
 Grade 2: Hold carfilzomib until \leq Grade 1 and resume at full carfilzomib dose
Tumor Lysis Syndrome (≥ 3 of the following: $\geq 50\%$ increase in creatinine, uric acid, or phosphate; $\geq 30\%$ increase in potassium; $\geq 20\%$ decrease in calcium; or 2-fold increase in LDH)	Hold carfilzomib until all abnormalities in serum chemistries have resolved. Resume at full dose
Herpes zoster or simplex of any grade	Hold carfilzomib until lesions are dry. Resume at full dose
Neuropathy	Grade 2 treatment emergent neuropathy with pain: Hold carfilzomib until resolved to \leq Gr 1 without pain. Then restart at next dose level reduction.
Congestive Heart Failure	Patients with clinical symptoms and/or significant changes in EF ($>10\%$) will hold carfilzomib and repeat cardioechogram as clinically appropriate; if persisting/worsening clinical symptoms and/or significant changes in EF that is attributed to the therapy, the patient will be taken off the trial.
Hypertension (uncontrollable by medications, hypertension emergencies, or >3 episodes of hypertension urgencies)	
Hypertension uncontrollable by medications or >3 episodes of hypertension urgencies – hold carfilzomib and decrease to next dose level.
 
Hypertension emergency – stop therapy and go off protocol

Myocardial infarction	Any patient experiencing myocardial infarction will stop therapy and go off protocol
Posterior reversible encephalopathy syndrome (PRES)	If PRES is suspected, hold carfilzomib. Consider evaluation with neuroradiological imaging, specifically MRI, for onset of visual or neurological symptoms suggestive of PRES. If PRES is confirmed, permanently discontinue carfilzomib. If the diagnosis of PRES is excluded, carfilzomib administration may resume at the same dose, if clinically appropriate.

Carfilzomib Toxicities	Specific Dosing Modifications
Thrombotic microangiopathy (TMA)	If the diagnosis is suspected, hold carfilzomib and manage per standard of care including plasma exchange as clinically appropriate. If TMA is confirmed, permanently discontinue carfilzomib. If the diagnosis is excluded, carfilzomib can be restarted.
Hepatitis B reactivation	Carriers of HBV who require treatment with Kyprolis should be closely monitored for signs and symptoms of active HBV infection throughout treatment. Any subject who becomes HBV DNA positive or develops reactivation of HBV should have carfilzomib treatment interrupted and receive appropriate anti-viral treatment as per a specialist in Hepatitis B.
Progressive Multifocal Leukoencephalopathy	Patients should be monitored for any new or worsening neurologic, cognitive or behavioral signs or symptoms that may be suggestive of PML as part of the differential diagnosis of CNS disorders. If PML is suspected, patients should be promptly referred to a specialist and appropriate diagnostic testing should be initiated. Discontinue Kyprolis if PML diagnosis is confirmed.

